7.7 Safety evaluation

7.7.1 Physical examination

At Visits 1 (or Visit 2 for consecutive subjects) to 18 (or discontinuation of the treatment or tapering period) and Visit 19, the principal investigator or sub-investigator will examine the subject by the standard methods in use at the relevant institution, and will ascertain the occurrence or non-occurrence of adverse events.

When an adverse event is found, the details will be recorded in the CRF. If necessary, examination appropriate to the signs and symptoms will also be performed, as judged appropriate by a physician. For 2 weeks after the initial administration of the study drug, the subject's progression will be monitored with special care.

7.7.2 Columbia Suicide Severity Rating Scale (C-SSRS)

At Visits 1 (or Visit 2 for consecutive subjects) to 18 (or discontinuation of the treatment or tapering period), the principal investigator or sub-investigator will evaluate suicidal thinking using a questionnaire. For consecutive subjects, a measurement at Visit 9 in the preceding study may be used as a measurement at Visit 2 of this study. The date and results of evaluation will be recorded in the CRF. The principal investigator or sub-investigator will judge whether any abnormal change from baseline (Visit 2) is clinically significant (refer to Section 7.7.7.7) and will record any changes judged to be clinically significant as adverse events.

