- Tapering period: In order to minimize the occurrence of adverse events due to discontinuation of administration, a 1- to 2-week tapering period is set for subjects who complete the treatment period, or who withdraw from it during the second week or later. Subjects whose duloxetine dose at discontinuation or completion of the treatment period is 60 mg/day will receive 40 mg/day for one week then 20 mg/day for one week. If the dose at discontinuation or completion is 40 mg/day, 20 mg/day will be administered for one week.
- Follow-up period: No study drugs will be administered during the 1-week follow-up period. This period is set to enable evaluation of any adverse events during the week after completion of study drug administration, irrespective of whether or not the dose was tapered. If administration is discontinued during the treatment period, and there is then no administration during the tapering period, a 1-week follow-up period will be set after administration discontinuation.

The study design is shown in Fig. 3-1. The study schedule is shown in Appendix 1.

Fig. 3-1. Schematic diagram of study schedule

Until 50 weeks after treatment initiation, the dose may be increased to 40 mg/day or 60 mg/day as appropriate, depending on the symptoms.

Consecutive subjects will start this study from Visit 2 after completing Visit 9 in the preceding study.

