7.7.7 Evaluation of adverse events

7.7.7.1 Evaluation methods for adverse events

An adverse event is any unfavorable medical event suffered by someone administered a pharmaceutical product (including a study drug) and does not necessarily have a causal relationship with the relevant pharmaceutical product. In other words, an adverse event is any unfavorable and/or unexpected sign (including abnormal laboratory test result), symptom, or disease associated with the administration of a drug, irrespective of any causal relationship with that drug. Surgery that was already planned is not considered to be an adverse event, unless it leads to exacerbation of an existing disease, and is therefore not considered to be a serious adverse event even if it necessitates hospitalization. However, if an additional surgery is performed in connection with the planned surgery, this is taken to be an adverse event, and to be a serious adverse event if prolongation of hospitalization is required, or if any other criterion for being a serious adverse event is met. Hospitalization or prolongation of hospitalization for reasons other than adverse events is not considered to constitute a serious adverse event.

The presence or absence of an adverse event will be confirmed on the basis of the subject's spontaneous complaint, non-inductive questions, examination, C-SSRS, blood pressure, pulse rate, body weight, and ECG or laboratory test results. Adverse events include new onset of an event, increase in the severity or frequency of an event since administration initiation, and diagnostic abnormality, including abnormal laboratory test results. A symptom recorded as a medical history at study initiation will be handled as an adverse event only when symptoms are aggravated. In addition, loss of efficacy, and changes in the primary disease (depression) or scores for any of the CDRS-R items, will not be handled as adverse events in this study, unless judged to be serious adverse events.

The principal investigator or sub-investigator will evaluate adverse events. The principal investigator or sub-investigator will carefully investigate each adverse event, and record in the CRF the date of onset, time of onset, date of cessation (if the outcome is recovery or death), severity, seriousness (including the reason for judging seriousness), causal relationship with the study drug, actions taken for the adverse event, and outcome of the adverse event.

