- i Blood samples for quantitation of plasma concentrations of duloxetine will be collected for five times at any timing between Visit 5 and the completion of study drug administration during the treatment period. If the dose is increased or decreased, blood samples should be collected at least 2 weeks after the dose adjustment. Of five random blood samples, one or two samples should be collected before dosing.
- j Adverse events occurring within 7 days after the final administration of the study drug will be investigated. The subject is checked by telephone or other appropriate method, even if he/she fails to make a visit.
- k Dispense study drugs for tapering period.
- l If the tapering period is not conducted, the pregnancy test will be performed at Visit 17 or at the time of discontinuation during the treatment period.

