10.5 Analysis of Columbia suicide severity rating scale

Columbia Suicide Severity Rating Scale (C-SSRS) will be analyzed. The time-points for evaluation of C-SSRS are taken to be the screening period and all scheduled visits during the treatment period, and the final evaluation time (weeks 51-52 or at discontinuation of the treatment period or tapering period).

- 1) The distribution of categories (yes, no) on the below evaluation scale will be summarized in the form of a shift table before and after administration initiation as well as before administration initiation and the final evaluation time (weeks 51-52, or at discontinuation of the treatment period or tapering period). For categories before administration initiation, subjects with at least one “yes” assessment at any one evaluation time-point in the screening period or before administration initiation will be classified as “yes”, and other subjects will be classified as “no”. For categories

after administration initiation, subjects with at least one “yes” assessment at any one evaluation time-point after administration initiation will be classified as “yes”, and other subjects will be classified as “no”. Both before and after administration initiation as well as the final evaluation time, subjects with missing observed values at all evaluation time-points will be classified as “non-assessed subjects”.

- 2) The number and proportion of subjects in each category at each evaluation time-point will be determined.

Columbia suicide severity rating scale	
Suicidal ideation	1. Wish to be dead 2. Non-specific Active suicidal thoughts.
Suicidal behavior	1. Actual attempt 2. Non-Suicidal Self-Injurious Behavior 3. Self-Injurious Behavior, intent unknown 4. Interrupted attempt 5. Aborted attempt 6. Preparatory Act or Behavior 7. Suicidal behavior 8. Completed suicide

- 3) For the following five questions about suicidal ideation, the distribution on the highest question number with at least one “yes” answer will be summarized in the form of a shift table of before versus after administration initiation.

Question No.	Questions
1	Wish to be dead
2	Non-specific Active suicidal thoughts.
3	Active suicidal ideation with any methods (not plans) but without intent to act
4	Active suicidal ideation with some intent to act, without specific plan
5	Active suicidal ideation with specific plan and intent

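### The last scheduled C-SSRS is at Visit 18 or discontinuation, so most of the one-week follow-up off study drug has no structured suicidality measure

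*Protocol*

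**What the plan says.** Protocol 7.7.2 schedules the C-SSRS from the first visit "to 18 (or discontinuation of the treatment or tapering period), the principal investigator or sub-investigator will evaluate suicidal thinking using a questionnaire". The neighbouring section 7.7.1, on physical examination, gives the same span of visits and then adds Visit 19 by name.

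SAP 10.5 defines the C-SSRS time-points as "taken to be the screening period and all scheduled visits during the treatment period, and the final evaluation time", and places that final evaluation at weeks 51 to 52 or at discontinuation. The C-SSRS row in SAP Appendix 1 ends at Visit 18.

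Protocol 3.1 describes what follows: "No study drugs will be administered during the 1-week follow-up period". The stated purpose is to evaluate "any adverse events during the week after completion of study drug administration, irrespective of whether or not the dose was tapered". Section 7.7.7.2 accordingly runs adverse event assessment to 7 days after the final dose. A subject who misses Visit 19 is still contacted; footnote j of Appendix 1 says: "The subject is checked by telephone or other appropriate method, even if he/she fails to make a visit".

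Section 7.7.7.6 lists one class of adverse event of special concern, suicide-related events, and relies on the C-SSRS as set out in 7.7.2 to evaluate suicidal thinking.

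**The concern.** The follow-up week was planned to detect events after the last dose, and suicide-related events are the ones the protocol singles out. Yet the instrument chosen for them is not scheduled at the visit that closes the week. The CDRS-R and CGI-S stop earlier still, at Visit 17, so Visit 19 has no structured mood or suicidality scale.

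At stake is how the C-SSRS results can be read. The shift tables and by-visit counts in SAP 10.5 cannot register ideation or behaviour that begins after Visit 18 or discontinuation. Open questioning may be less sensitive than the scale for non-serious ideation. Section 7.7.7.1 says changes in the underlying depression are not handled as adverse events unless serious, whereas 7.7.2 gives the C-SSRS its own route to an adverse event record. That new ideation could go unrecorded for this reason is an inference, not something the documents state.

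**Working it through.** There is no planned figure to reproduce. The check compares the schedules and then counts days.

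**Schedules**

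| Source | C-SSRS at Visit 19? |
|---|---|
| Protocol 7.7.2 | No; ends at Visit 18 or discontinuation |
| SAP 10.5 | No; ends at weeks 51 to 52 or discontinuation |
| SAP Appendix 1 | No; 15 marks over 16 visit columns |
| Protocol Appendix 1, as it reads in the PDF text | Apparently yes; 16 marks over 16 visit columns |

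The 16 columns are 19 visits less the three that share a column (9/10, 12/13, 15/16). The last row conflicts with the other three but may be a reading error. In the same table the adherence row also runs to Visit 19, which the SAP copy does not show. The ECG marks fall under Visits 9/10 and 12/13, where 7.7.5 says Visit 11.

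**Days between the last C-SSRS and Visit 19**

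Inputs are from protocol Table 7-3: Visit 17 on Day 350; Visit 18 at 7 days (last dose 40 mg) or 14 days (60 mg) after it, ±3 days; discontinuation assessment at the last dose, +3 days; Visit 19 on day 7 or later after the last dose. I assume a completed taper ends on the nominal Visit 18 day.

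- Last dose 40 mg: Visit 18 = 350 + 7 = 357, window 354 to 360. Visit 19 is at 357 + 7 = 364 or later. Gap = 364 − 357 = 7 days; range 364 − 360 = 4 to 364 − 354 = 10.
- Last dose 60 mg: Visit 18 = 350 + 14 = 364, window 361 to 367. Visit 19 is at 364 + 7 = 371 or later. Gap = 7 days; range 371 − 367 = 4 to 371 − 361 = 10.
- No taper, last dose on day D: last C-SSRS at D to D + 3, Visit 19 at D + 7 or later. Gap = 4 to 7 days.

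Table 7-3 sets no upper limit for Visit 19, so these gaps are for the earliest permitted visit. Of the 7 days after the last dose, between 7 − 3 = 4 and 7 − 0 = 7 follow the last scheduled C-SSRS.

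**Coverage before that point.** Visits 3 to 18 give 18 − 3 + 1 = 16 scheduled post-baseline assessments.

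**Who is most affected.** A tapered subject has a C-SSRS at the end of treatment and another at Visit 18, after the step-down has begun. A subject who stops without a taper has only the one at discontinuation. Under 3.1 and 5.2 this applies to withdrawal before the second week, and to serious reactions, safety problems or refusal of the taper. Planned dropout is 25% of 135 = 33.75, about 34 subjects. The documents do not say how many of these would skip the taper, and completers may skip it too, so no firm number can be given.

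**The case against.** The strongest reply is that this is a scheduling choice and leaves no blind spot. At Visit 19 the investigator examines the subject and asks about adverse events, by telephone if necessary. Suicide-related events are reported to the sponsor and sent promptly to the Safety Evaluation Committee. The SAP tabulates the Suicide/self-injury SMQ with a broad search. All of this stands. A reader might infer that suicidality goes unmeasured after the last dose; the documents support only that it is not measured with the C-SSRS.

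A reader might also see a contradiction with 7.7.7.1, which names "non-inductive questions, examination, C-SSRS, blood pressure, pulse rate, body weight, and ECG or laboratory test results" among the means of confirming adverse events. That is one general list, tied to no visit. Blood pressure, pulse rate, body weight, ECG and laboratory tests are in it too, and none is scheduled at Visit 19. Applying the list to the follow-up week is the reader's inference, so the point does not rest on it.

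Two further readings go too far. It is not true that no day of the week can contain a C-SSRS, since the +3 day allowance may place the last one inside it. Nor is this the only period aimed at discontinuation effects: 3.1 sets the taper for that purpose, SAP 10.1 item 6 analyses tapering events, and the Visit 18 C-SSRS comes at its end.

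The objection also bears on the remedy. The prohibition on antidepressants and most other listed drugs in 6.2.1 ends at Visit 18, so answers at Visit 19 may reflect new treatment. Adding them to the any-time-after-initiation category would blur those tables, with no control arm to separate the effects. This stands and shapes the fix.

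**Conclusion.** The point holds in a limited form. By protocol 7.7.2, SAP 10.5 and SAP Appendix 1, no C-SSRS is scheduled after Visit 18 or discontinuation, which leaves 4 to 7 of the 7 days after the last dose without a structured suicidality measure. That 7.7.1 names Visit 19 while 7.7.2 does not, and that the week exists to evaluate adverse events whether or not the dose was tapered, makes this worth correcting.

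The consequence is confined to what the C-SSRS tables can show. Suicide-related adverse events can still be captured, and no sample size, power, error rate or analysis set is affected. The day count assumes that the taper ends on the nominal Visit 18 day and visits keep to Table 7-3. If the protocol Appendix 1 mark at Visit 19 is genuine, the schedule contradicts 7.7.2, and SAP 10.5 has no time-point for the data it would collect. The passages would then need reconciling in any case.

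**What to change.** 1. Add the C-SSRS at Visit 19 to protocol 7.7.2, covering the time since the last assessment, by telephone if the subject does not attend.
2. Check the C-SSRS row of protocol Appendix 1 against the source table, and make it, 7.7.2, SAP 10.5 and SAP Appendix 1 agree.
3. Add Visit 19 to the SAP 10.5 time-points. Show it as its own row in item 2 and as a separate follow-up category beside the shift tables. Keep it out of the after-initiation category in items 1, 3 and 4.
4. Show treatment started after Visit 18 alongside the Visit 19 results; protocol 6.2 already records concomitant treatment to Visit 19.

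The cost is a protocol amendment with IRB approval, a CRF change, and a few minutes per subject at a contact that already takes place. Where follow-up is already over, the remaining step is to state in the report that the C-SSRS tables end at Visit 18 or discontinuation.

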7.7.3 Body weight

Body weight (kg) will be measured at Visits 2, 5, 8, 11, 14, 17 (or at discontinuation of the treatment period) and Visit 18 (or at discontinuation of the tapering period). For consecutive subjects, a measurement at Visit 9 in the preceding study may be used as a measurement at Visit 2 of this study. The date and result of measurement will be recorded in the CRF. The principal investigator or sub-investigator will judge whether any abnormal change from baseline (Visit 2) is clinically significant (refer to Section 7.7.7.7) and will record any changes judged to be clinically significant as adverse events.

7.7.4 Blood pressure and pulse rate

The blood pressure (systolic and diastolic) and pulse rate, at rest, will be measured at Visits 1 (new subjects only), 2, 5, 8, 11, 14, 17 (or at discontinuation of the treatment period) and Visit 18 (or at discontinuation of the tapering period). For consecutive subjects, a measurement at Visit 9 in the preceding study may be used as a measurement at Visit 2 of this study. The date and result of measurement will be recorded in the CRF. The principal investigator or sub-investigator will judge whether any abnormal change from baseline (Visit 2) is clinically significant (refer to Section 7.7.7.7) and will record any changes judged to be clinically significant as adverse events.

7.7.5 Electrocardiogram

Standard, 12-lead electrocardiogram (ECG) will be performed at Visits 1 (or Visit 2 for consecutive subjects), 5, 11, and 18 (or at discontinuation of the tapering period; if not transferred to the tapering period, at completion or discontinuation [Visit 17] of the treatment period). For consecutive subjects, a measurement at Visit 9 in the preceding study may be used as a measurement at Visit 2 of this study. The principal investigator or sub-investigator will judge whether ECG results are normal or abnormal, and will record the date of ECG, the judgment, and any abnormal findings in the CRF.

If there are abnormal findings, the principal investigator or sub-investigator will judge whether the abnormal change from baseline (i.e., Visit 1 for new subjects or Visit 2 for consecutive subjects) is clinically significant (refer to Section 7.7.7.7), and will record any changes judged to be clinically significant as adverse events.

7.7.6 Laboratory tests

7.7.6.1 Laboratory test items

At Visits 1 (or Visit 2 for consecutive subjects), 5, 8, 11, 14, and 18 (or at discontinuation of the tapering period; if not transferred to the tapering period, at completion or discontinuation [Visit 17] of the treatment period), blood samples will be collected for laboratory tests, the volumes being 2 mL for hematology tests, and 8 mL and 5 mL for blood chemistry tests, at Visit 1 and other visits, respectively; and urine samples will also be collected. The samples will then be sent to the clinical laboratory facility specified in Section 7.7.6.2. Details of the collection, handling, storage, and shipment of samples are stipulated in a separate document. For new subjects, blood samples and urine samples at Visit 1 will be collected after obtaining informed consent, between 3 weeks before the initial administration of the study drug and Visit 2. For consecutive subjects, a measurement at Visit 9 in the preceding study may be used as a measurement at Visit 2 of this study. Both new subjects and consecutive subjects will be registered after the latest measurements at Visit 2 are confirmed.

The principal investigator or sub-investigator will judge whether the abnormal change from baseline (i.e., Visit 1 for new subjects or Visit 2 for consecutive subjects) is clinically significant (refer to Section 7.7.7.7), and will record any changes judged to be clinically significant as adverse events. The sample collection dates will be recorded in the CRF for each sample type (blood or urine).

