12) For new subjects, either (i) suicidal ideation and/or suicidal attempt within 1 year before Visit 1; or (ii) at Visits 1 and 2 (or Visit 2 for consecutive subjects), answer "Yes" to questions 4 and/or 5 about suicidal ideation, and/or any of the questions about suicidal behaviors (except those about non-suicidal self-injurious behavior), on the Columbia suicide severity rating scale (C-SSRS).	X	X
13) Body weight below 20 kg at Visit 2.	X	X
14) Serious ^{*1} or medically unstable ^{*2} disease (cardiovascular disease, hepatic	X	X

Exclusion criteria	Consecutive subjects	New subjects

disease, respiratory disease, hematologic disease, endocrine disease, peripheral vascular disorder, neuropsychiatric disease, renal disease), or clinically problematic abnormal laboratory test results or abnormal electrocardiography (ECG) findings*³.
 
*1: Grade 3 in "Concerning classification criteria for seriousness of adverse drug reactions to pharmaceutical products, etc." (Drug Safety Notification no. 80; June 29, 1992).
 
*2: Judged by the principal investigator or sub-investigator to have the potential to disrupt study participation, or to necessitate hospitalization during the study period.
 
*3: Judged by the principal investigator or sub-investigator to suggest serious medical problems, or to necessitate aggressive therapy.
		

15) Meeting one or more of the following criteria:
 
 At Visit 2, latest ALT or AST of 100 U/L or higher, or latest total bilirubin of 1.6 mg/dL or higher. Latest serum creatinine level of 2.0 mg/dL or higher at Visit 2. Or have severe renal impairment, history of renal transplantation, and/or currently undergoing renal dialysis. 	X	X
16) Glaucoma, elevated intraocular pressure, and/or prostatic hypertrophy or other types of dysuria.	X	X
17) Depression or depressive state due to organic brain disorder.	X	X
18) Hemorrhagic tendency or hemorrhagic diathesis.	X	X
19) Treatment with monoamine oxidase (MAO) inhibitor within 14 days before Visit 2, and/or potential for MAO inhibitor treatment during the study period or within 5 days after completion of study drug administration.	X	X
20) Hypersensitivity to duloxetine or inactive ingredients of duloxetine formulation.	X	X
21) Allergic to two or more drugs, or a history of serious allergic reactions to one or more drugs.	X	X

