8.11.3 Laboratory test results

Summary statistics will be calculated for the measurements and change from baseline at each time-point.

The baseline is defined as Visit 1 for new subjects or Visit 2 for consecutive subjects.

The category distribution of the qualitative laboratory test data at each time-point will be summarized.

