6.3 Assessments, observations and tests: Permitted timing and handling in statistical analyses

In principle, data obtained at the time-points shown in the case report forms, and collected in accordance with the performance schedule shown in the study protocol, will be used for the statistical analysis. In the case of data reported at the discontinuation visit, the time-points for use in analyses will be determined on the basis of the permitted ranges in the performance schedule. If there is duplication by data obtained at the scheduled visits and data obtained at the discontinuation tests, the data obtained closest to the scheduled date will be used. If this does not eliminate duplication, data from the scheduled visit will be used. Unscheduled visits will not be included in the time-points for analysis. For the permitted ranges for the observation, test, and evaluation time-points shown in the study protocol, refer to Appendix 2.

For the final evaluation, data obtained at weeks 51 to 52 or at discontinuation of the treatment/tapering period will be used, except for CDRS-R and CGI-S scores, for which those obtained at week 50 or at discontinuation of the treatment period are used. However, if none of the above data are available, the latest data among reported data collected at scheduled visits are used for the final evaluation.

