6.5 Baseline

Data obtained before initiation of study drug administration (Visit 2) in this study will be used as baseline data, unless otherwise specified. As with laboratory test results of new subjects, if data from Visit 2 are missing, data from Visit 1 (screening period) will be used as baseline data. The baseline for the analysis of

data from the preceding study throughout this study will be the observed values obtained before initiation of study drug administration in the preceding study.

7. Subject composition and backgrounds

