10.3 Analysis of laboratory test results

The below laboratory test results will be analyzed. The time-points for evaluation of laboratory test results are taken to be baseline (Visit 1 for new subjects, Visit 2 for consecutive subjects), weeks 4, 16, 28, and 40 after administration initiation, and the final evaluation time (weeks 51-52, or at discontinuation of the treatment period or tapering period). However, for HbA_{1c} TSH, FT3 and FT4, evaluation is solely during the screening period.

Classification	Parameter
Hematology tests	Leukocyte count, erythrocyte count, hemoglobin, hematocrit, leukocyte fractions (eosinophils, basophils, neutrophils, monocytes, lymphocytes), platelet count
Blood chemistry	AST, ALT, LDH, γ -GTP, ALP, creatine kinase, total bilirubin, total protein, blood urea nitrogen, serum creatinine, uric acid, total cholesterol, triglycerides, Na, K, Cl, Ca, blood glucose, HbA _{1c} , TSH, FT3, FT4
Urinalysis (qualitative)	Urinary protein, urinary glucose, urobilinogen, urinary occult blood

- 1) With respect to laboratory test results obtained as continuous values, summary statistics of observed values at each evaluation time-point and changes from baseline will be calculated.
- 2) With respect to urinalysis parameters obtained as qualitative values, the number and proportion of subjects in each category at each evaluation time-point will be determined.
- 3) As evaluation of liver function, the numbers and proportions of subjects meeting the following criteria at each evaluation time-point, and the numbers and proportions meeting these criteria at least one evaluation time-point after administration initiation, will be determined:
 - AST >5 times the upper limit of the reference values.
 - ALT >5 times the upper limit of the reference values.
 - AST or ALT >3 times the upper limit of the reference values, and total bilirubin >2 times the

- upper limit of the reference values
 - AST >3 times the upper limit of the reference values.
 - ALT >3 times the upper limit of the reference values.
- 4) For consecutive subjects, summary statistics of observed values at each evaluation time-point in the preceding study and this study and changes from baseline in the preceding study will be calculated.

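### The laboratory baseline of new subjects is fixed at Visit 1 although entry rests on the latest value at Visit 2, so where a repeat pre-dose sample exists the change from baseline can start from the earlier, worse value

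*Protocol*

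**What the plan says.** **Entry.** Exclusion 15 in Protocol 4.3 applies its liver limits to the most recent result: "At Visit 2, latest ALT or AST of 100 U/L or higher, or latest total bilirubin of 1.6 mg/dL or higher". The renal limit works the same way: "Latest serum creatinine level of 2.0 mg/dL or higher at Visit 2". Section 7.7.6.1 adds "Both new subjects and consecutive subjects will be registered after the latest measurements at Visit 2 are confirmed".

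**Sampling.** In the schedule (Appendix 1 of both documents, footnote b) the Visit 2 laboratory test is for consecutive subjects only. New subjects have one scheduled pre-dose test, at Visit 1. Under 7.7.6.1 that sample may be drawn at any time after consent, from 3 weeks before the first dose up to Visit 2.

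**Baseline.** Three places use Visit 1 for new subjects:
- Protocol 8.11.3: "The baseline is defined as Visit 1 for new subjects or Visit 2 for consecutive subjects".
- SAP 10.3, which lists its time-points as "baseline (Visit 1 for new subjects, Visit 2 for consecutive subjects), weeks 4, 16, 28, and 40 after administration initiation".
- Protocol 7.7.6.1, where the investigator "will judge whether the abnormal change from baseline (i.e., Visit 1 for new subjects or Visit 2 for consecutive subjects) is clinically significant".

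SAP 6.5 takes pre-dose Visit 2 data unless otherwise specified. For the laboratory results of new subjects it adds that "if data from Visit 2 are missing, data from Visit 1 (screening period) will be used as baseline data".

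**Unscheduled data.** SAP 6.3: "Unscheduled visits will not be included in the time-points for analysis".

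**The concern.** The value that admits a new subject and the value from which that subject is analysed are chosen by different rules. With a single pre-dose sample they coincide and nothing is lost. If a subject failed a limit, was sampled again and was admitted on the second result, they differ in a known direction: for the parameter that failed, the earlier value is the worse one. The baseline is then not the last pre-dose value, and changes in that parameter lean toward improvement.

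Long-term safety is the primary objective, and change from baseline is one of the planned laboratory summaries. The Visit 1 baseline also enters the investigator's judgement of whether a laboratory change is clinically significant and so recorded as an adverse event. Separately, SAP 6.5 and SAP 10.3 can give different baselines for the same subject, so two analysts could produce different tables from the same data.

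**Working it through.** The plan gives no figure of its own on this point, so the check sets the rules side by side and then sizes the effect with assumed values.

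**1. Which value becomes baseline for a new subject?**

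| Pre-dose samples | 8.11.3 and SAP 10.3 | SAP 6.5 with 6.3 |
|---|---|---|
| One sample, recorded as Visit 1 | that value | that value |
| Visit 1 fails, repeat recorded at Visit 2 | failing value | repeat |
| Visit 1 fails, repeat recorded as unscheduled | failing value | failing value (Visit 2 missing, repeat not used) |
| Two samples in the Visit 1 window, both recorded as Visit 1 | not stated | not stated |

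The rules agree in row 1, conflict in row 2, agree on the earlier value in row 3, and are silent in row 4. The phrase unless otherwise specified in SAP 6.5 probably lets SAP 10.3 prevail in row 2, but the SAP does not say so.

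**2. Effect in one subject.** Let V1 be the earlier value, L the last pre-dose value and X the on-drug value.
- Planned change: X - V1. Change from the last pre-dose value: X - L.
- Difference: (X - V1) - (X - L) = -(V1 - L).
- For ALT, admission on a repeat means V1 of at least 100 U/L and L below 100 U/L, so the difference is always negative. The same holds for bilirubin around 1.6 mg/dL and creatinine around 2.0 mg/dL.
- A rise shows as a fall only if L < X < V1.

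Assumed ALT values in U/L, since the documents hold no patient data:

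| V1 | L | X | X - V1 | X - L | Reading |
|---|---|---|---|---|---|
| 110 | 60 | 90 | -20 | +30 | sign reversed |
| 120 | 60 | 95 | -25 | +35 | sign reversed |
| 120 | 60 | 130 | +10 | +70 | understated by 60 |
| 120 | 60 | 250 | +130 | +190 | understated by 60 |

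**3. Effect on the mean change.** With k subjects admitted on a repeat, n analysed and a mean gap g = V1 - L, the shift is -k × g / n. SAP 6.1 presents results on the whole analysis set unless otherwise specified, and SAP 10.3 does not split the change-from-baseline tables of this study by subject type. So n lies between about 135 (target registered) and 100 (target completing one year). The values of k and g are assumed.
- k = 1, g = 60, n = 135: -60/135 = -0.44 U/L.
- k = 5, g = 60, n = 100: -300/100 = -3.0 U/L.
- Extremes for g from 20 to 120: -20/135 = -0.15 and -600/100 = -6.0 U/L.

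If new subjects were tabulated alone, with an assumed n = 70 and g = 50, the shift would be -50/70 = -0.71 (k = 1) to -250/70 = -3.57 U/L (k = 5).

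**The case against.** The strongest reply is that retesting is inferred. No section describes repeating a failed screening test. Because new subjects have no scheduled Visit 2 laboratory test and consecutive subjects may bring forward a result from the preceding study, a single eligibility sentence covering both groups would have to speak of the latest result. For most new subjects that is simply the Visit 1 result. A repeat drawn before Visit 2 also falls inside the Visit 1 window and might itself be recorded as Visit 1. This stands, and it limits the point to subjects who have a repeat. It does not settle the matter, because nothing says which of two values counts.

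Three stronger readings are tempting, and the documents do not support them.
- A reader might infer that the plan always analyses retested subjects from the failing value. It can do so, but SAP 6.5 would take a repeat recorded at Visit 2, and the window leaves the case of two Visit 1 samples open.
- A reader might infer that rises on drug generally appear as falls. That needs an on-drug value between the two pre-dose values. Larger rises still show as rises, only smaller.
- A reader might infer that liver signals or adverse events are hidden. The observed-value summaries and the >3 and >5 times upper-limit tables in SAP 10.3 do not use baseline. Nor do the hepatic criterion for serious events in 7.7.7.8.1 or the criteria in Appendix 2. Section 7.7.7.7 also lists conditions, such as need for treatment or for a further test, that make a finding clinically significant whatever the baseline. Only the remaining discretionary judgement leans on it.

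Two further replies have some weight. Exclusion 14 separately removes clinically problematic laboratory abnormalities, which may shrink the affected group. And a repeat that counts because it passed is selected to be low, so using it as baseline has a small bias of its own, toward apparent worsening.

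**Conclusion.** The point holds in a narrow form. The baseline rule for new subjects' laboratory tests is inconsistent within the SAP, and it is not the last pre-dose value whenever a usable repeat exists. In such a subject the change in the failing parameter is understated by exactly V1 - L. In the pooled mean, a plausible shift is about -0.4 to -3.0 U/L for ALT, if 1 to 5 subjects are affected with a 60 U/L gap. The documents give neither the number of new subjects nor the number retested, and the affected group is probably small. No planned test depends on these means. This is a minor point, worth correcting because it touches safety and costs little.

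**What to change.** In Protocol 8.11.3 and SAP 6.5 and 10.3, define the laboratory baseline of new subjects as the last recorded value before the first dose, including repeat samples. In SAP 6.3, exempt pre-dose repeats from the rule on unscheduled visits for this purpose. Reconcile the baseline wording in Protocol 7.7.6.1 with the same definition, so that the tables and the investigator's comparison use one reference.

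Confirm that repeat results enter the laboratory data with their sampling dates. Protocol 9.7.3 lists laboratory results as external data, but no section says that repeats are included.

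The cost is a sentence or so in each section and a data-transfer check. Subjects with a single pre-dose sample are unaffected. The small downside is the selection effect noted above: changes in the few retested subjects may tilt slightly toward worsening. Listing both pre-dose values for those subjects would make this visible.
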